5.2 SAFETY PARAMETERS AND DEFINITIONS

Safety assessments will consist of monitoring and recording adverse events, including serious adverse events and adverse events of special interest, performing protocol-specified safety laboratory assessments, measuring protocol-specified vital signs, and conducting other protocol-specified tests that are deemed critical to the safety evaluation of the study.

Certain types of events require immediate reporting to the Sponsor, as outlined in Section 5.4.

5.2.1 Adverse Events

According to the ICH guideline for Good Clinical Practice, an adverse event is any untoward medical occurrence in a clinical investigation patient administered a pharmaceutical product, regardless of causal attribution. An adverse event can therefore be any of the following:

- Any unfavorable and unintended sign (including an abnormal laboratory finding), symptom, or disease temporally associated with the use of a medicinal product, whether or not considered related to the medicinal product
- Any new disease or exacerbation of an existing disease (a worsening in the character, frequency, or severity of a known condition) (see Sections [5.3.5.9](#) and [5.3.5.10](#) for more information)
- Recurrence of an intermittent medical condition (e.g., headache) not present at baseline
- Any deterioration in a laboratory value or other clinical test (e.g., ECG, X-ray) that is associated with symptoms or leads to a change in study treatment or concomitant treatment or discontinuation from study drug
- Adverse events that are related to a protocol-mandated intervention, including those that occur prior to assignment of study treatment (e.g., screening invasive procedures such as biopsies)

5.2.2 Serious Adverse Events (Immediately Reportable to the Sponsor)

A serious adverse event is any adverse event that meets any of the following criteria:

- Is fatal (i.e., the adverse event actually causes or leads to death)
- Is life threatening (i.e., the adverse event, in the view of the investigator, places the patient at immediate risk of death)

This does not include any adverse event that, had it occurred in a more severe form or was allowed to continue, might have caused death.

- Requires or prolongs inpatient hospitalization (see Section [5.3.5.10](#))
- Results in persistent or significant disability/incapacity (i.e., the adverse event results in substantial disruption of the patient's ability to conduct normal life functions)
- Is a congenital anomaly/birth defect in a neonate/infant born to a mother exposed to study drug
- Is a significant medical event in the investigator's judgment (e.g., may jeopardize the patient or may require medical/surgical intervention to prevent one of the outcomes listed above)

The terms "severe" and "serious" are not synonymous. Severity refers to the intensity of an adverse event (e.g., rated as mild, moderate, or severe, or according to DAIDS Table v2.1 toxicity scale; see Section [5.3.3](#)); the event itself may be of relatively minor medical significance (such as severe headache without any further findings).

Severity and seriousness need to be independently assessed for each adverse event recorded on the eCRF.

Serious adverse events are required to be reported by the investigator to the Sponsor immediately (i.e., no more than 24 hours after learning of the event; see Section 5.4.2 for reporting instructions).

5.2.3 Adverse Events of Special Interest (Immediately Reportable to the Sponsor)

Adverse events of special interest are required to be reported by the investigator to the Sponsor immediately (i.e., no more than 24 hours after learning of the event; see Section 5.4.2 for reporting instructions). Adverse events of special interest for this study are as follows:

- [REDACTED]
- Clinically significant Grade ≥ 3 adverse event, as determined by the investigator
- [REDACTED]
 - [REDACTED]
 - [REDACTED]
 - [REDACTED]
- [REDACTED]
- Cases of potential drug-induced liver injury that include an elevated ALT or AST in combination with either an elevated bilirubin or clinical jaundice, as defined by Hy's Law (see Section 5.3.5.6)
- Suspected transmission of an infectious agent by the study drug, as defined below
Any organism, virus, or infectious particle (e.g., prion protein transmitting transmissible spongiform encephalopathy), pathogenic or non-pathogenic, is considered an infectious agent. A transmission of an infectious agent may be suspected from clinical symptoms or laboratory findings that indicate an infection in a patient exposed to a medicinal product. This term applies only when a contamination of the study drug is suspected.

5.3 METHODS AND TIMING FOR CAPTURING AND ASSESSING SAFETY PARAMETERS

The investigator is responsible for ensuring that all adverse events (see Section 5.2.1 for definition) are recorded on the Adverse Event eCRF and reported to the Sponsor in accordance with instructions provided in this section and in Sections 5.4–5.6. The investigator is also responsible for reporting medical device complaints (see Section 5.4.4).

For each adverse event recorded on the Adverse Event eCRF, the investigator will make an assessment of seriousness (see Section 5.2.2 for seriousness criteria), severity (see Section 5.3.3), and causality (see Section 5.3.4).

5.3.1 Adverse Event Reporting Period

Investigators will seek information on adverse events at each patient contact. All adverse events, whether reported by the patient or noted by study personnel, will be recorded in the patient's medical record and on the Adverse Event eCRF.

After informed consent has been obtained but prior to initiation of study drug, only serious adverse events caused by a protocol-mandated intervention (e.g., invasive procedures such as biopsies, discontinuation of medications) should be reported (see Section 5.4.2 for instructions for reporting serious adverse events).

After initiation of study drug, all adverse events will be reported until 28 days after the final dose of study drug.

Instructions for reporting adverse events that occur after the adverse event reporting period are provided in Section 5.6.

5.3.2 Eliciting Adverse Event Information

A consistent methodology of non-directive questioning should be adopted for eliciting adverse event information at all patient evaluation timepoints. Examples of non-directive questions include the following:

"How have you felt since your last clinic visit?"

"Have you had any new or changed health problems since you were last here?"

5.3.3 Assessment of Severity of Adverse Events

The investigator will use the DAIDS toxicity grading scale (HHS 2017), with slight modifications for clarity and for alignment with internal practices (see [Appendix 10](#)), for assessing the severity of each adverse event reported during the study. The investigator will use the grading scale in [Table 5](#) for assessing the severity of adverse events that are not specifically listed in the DAIDS toxicity grading scale.

Table 5 Adverse Event Severity Grading Scale for Events Not Specifically Listed in DAIDS Toxicity Grading Scale

Grade	Severity
1	Mild; transient or mild discomfort (<48 hours); no medical intervention or therapy required
2	Moderate; mild to moderate limitation in activity; some assistance may be needed; no or minimal medical intervention or therapy required
3	Severe; marked limitation in activity; some assistance usually required; medical intervention or therapy required; hospitalization possible
4	Life-threatening; extreme limitation in activity; significant assistance required; significant medical intervention or therapy required, hospitalization or hospice care probable

DAIDS=Division of AIDS.

Notes: Developed by the Division of AIDS, National Institute of Allergy and Infectious Diseases, National Institutes of Health, U.S. Department of Health and Human Services.

Regardless of severity, some events may also meet seriousness criteria. Refer to definition of a serious adverse event (see Section [5.2.2](#)).

5.3.4 Assessment of Causality of Adverse Events

Investigators should use their knowledge of the patient, the circumstances surrounding the event, and an evaluation of any potential alternative causes to determine whether an adverse event is considered to be related to the study drug, indicating "yes" or "no" accordingly. The following guidance should be taken into consideration (see also [Table 6](#)):

- Temporal relationship of event onset to the initiation of study drug
- Course of the event, with special consideration of the effects of dose reduction, discontinuation of study drug, or reintroduction of study drug (as applicable)
- Known association of the event with the study drug or with similar treatments
- Known association of the event with the disease under study
- Presence of risk factors in the patient or use of concomitant medications known to increase the occurrence of the event
- Presence of non-treatment-related factors that are known to be associated with the occurrence of the event

Table 6 Causal Attribution Guidance

Is the adverse event suspected to be caused by the study drug on the basis of facts, evidence, science-based rationales, and clinical judgment?	
YES	There is a plausible temporal relationship between the onset of the adverse event and administration of the study drug, and the adverse event cannot be readily explained by the patient's clinical state, intercurrent illness, or concomitant therapies; and/or the adverse event follows a known pattern of response to the study drug; and/or the adverse event abates or resolves upon discontinuation of the study drug or dose reduction and, if applicable, reappears upon re-challenge.
NO	An adverse event will be considered related, unless it fulfills the criteria specified below. Evidence exists that the adverse event has an etiology other than the study drug (e.g., preexisting medical condition, underlying disease, intercurrent illness, or concomitant medication); and/or the adverse event has no plausible temporal relationship to administration of the study drug (e.g., cancer diagnosed 2 days after first dose of study drug).

5.3.5 Procedures for Recording Adverse Events

Investigators should use correct medical terminology/concepts when recording adverse events on the Adverse Event eCRF. Avoid colloquialisms and abbreviations.

Only one adverse event term should be recorded in the event field on the Adverse Event eCRF.

5.3.5.1 Diagnosis versus Signs and Symptoms

A diagnosis (if known) should be recorded on the Adverse Event eCRF rather than individual signs and symptoms (e.g., record only liver failure or hepatitis rather than jaundice, asterixis, and elevated transaminases). However, if a constellation of signs and/or symptoms cannot be medically characterized as a single diagnosis or syndrome at the time of reporting, each individual event should be recorded on the Adverse Event eCRF. If a diagnosis is subsequently established, all previously reported adverse events based on signs and symptoms should be nullified and replaced by one adverse event report based on the single diagnosis, with a starting date that corresponds to the starting date of the first symptom of the eventual diagnosis.

5.3.5.2 Adverse Events That Are Secondary to Other Events

In general, adverse events that are secondary to other events (e.g., cascade events or clinical sequelae) should be identified by their primary cause, with the exception of severe or serious secondary events. A medically significant secondary adverse event that is separated in time from the initiating event should be recorded as an independent event on the Adverse Event eCRF. For example:

- If vomiting results in mild dehydration with no additional treatment in a healthy adult, only vomiting should be reported on the eCRF.

- If vomiting results in severe dehydration, both events should be reported separately on the eCRF.
- If a severe gastrointestinal hemorrhage leads to renal failure, both events should be reported separately on the eCRF.
- If dizziness leads to a fall and consequent fracture, all three events should be reported separately on the eCRF.
- If neutropenia is accompanied by an infection, both events should be reported separately on the eCRF.

All adverse events should be recorded separately on the Adverse Event eCRF if it is unclear as to whether the events are associated.

5.3.5.3 Persistent or Recurrent Adverse Events

A persistent adverse event is one that extends continuously, without resolution, between patient evaluation timepoints. Such events should only be recorded once on the Adverse Event eCRF. The initial severity (intensity or grade) of the event will be recorded at the time the event is first reported. If a persistent adverse event becomes more severe, the most extreme severity should also be recorded on the Adverse Event eCRF. If the event becomes serious, it should be reported to the Sponsor immediately (i.e., no more than 24 hours after learning that the event became serious; see Section 5.4.2 for reporting instructions). The Adverse Event eCRF should be updated by changing the event from "non-serious" to "serious," providing the date that the event became serious, and completing all data fields related to serious adverse events.

A recurrent adverse event is one that resolves between patient evaluation timepoints and subsequently recurs. Each recurrence of an adverse event should be recorded as a separate event on the Adverse Event eCRF.

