2. OBJECTIVES AND ENDPOINTS

This Phase IIa, multicenter, randomized, double-blind, placebo-controlled, crossover study will evaluate the efficacy, safety, pharmacokinetics, and pharmacodynamic (PD) effects of GDC-6599 compared with placebo in patients with a history of chronic cough. It will assess the potential benefit of GDC-6599 to reduce cough frequency and severity in patients with a diagnosis of CRC with asthma, UCC, or CRC with COPD. The study will also *explore the effects* of GDC-6599 on mannitol-induced cough and/or AHR and the value of mannitol-induced cough hypersensitivity and/or AHR as a prognostic tool in patients with CRC with asthma, UCC, or CRC with COPD as a measure of TRPA1 airway activity. Specific objectives and corresponding endpoints for the study are outlined in [Table 1](#) below.

Table 1 Objectives and Corresponding Endpoints

Primary Objective	Corresponding Endpoint
• To evaluate the efficacy of GDC-6599, as compared with placebo, in patients with CRC with asthma or UCC	• Change in cough frequency per hour, assessed objectively over 24 hours (24-hour OCC) using VitaloJAK® cough recorder, from baseline to Day 14
Secondary Objective	Corresponding Endpoints
• To evaluate the efficacy of GDC-6599, as compared with placebo, in patients with CRC with asthma or UCC	• Change in the severity of cough, as assessed through the use of the patient-reported cough severity VAS and NRS scores, from baseline to Day 14
Safety Objective	Corresponding Endpoints
• To evaluate the safety of GDC-6599 compared with placebo	• Incidence and severity of adverse events, with severity determined according to the DAIDS toxicity grading scale ^a • Change from baseline in targeted vital signs • Change from baseline in targeted clinical laboratory test results
Pharmacokinetic Objective	Corresponding Endpoints
• To characterize the PK profile of GDC-6599	• Plasma concentration of GDC-6599 at specified timepoints
Exploratory Objectives	Corresponding Endpoints
• To evaluate mannitol-induced cough response as a measure of TRPA1 airway activity and treatment benefit of GDC-6599, as compared with placebo, in patients with CRC with asthma or UCC	• Change in cough hypersensitivity to mannitol, measured as the CDR to mannitol, from baseline to Day 14

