5.3.5.4 Abnormal Laboratory Values

Not every laboratory abnormality qualifies as an adverse event. A laboratory test result must be reported as an adverse event if it meets any of the following criteria:

- Is accompanied by clinical symptoms
- Results in a change in study treatment (e.g., dosage modification, treatment interruption, or treatment discontinuation)
- Results in a medical intervention (e.g., potassium supplementation for hypokalemia) or a change in concomitant therapy
- Is clinically significant in the investigator's judgment

It is the investigator's responsibility to review all laboratory findings. Medical and scientific judgment should be exercised in deciding whether an isolated laboratory abnormality should be classified as an adverse event.

If a clinically significant laboratory abnormality is a sign of a disease or syndrome (e.g., ALP and bilirubin 5× ULN associated with cholestasis), only the diagnosis (i.e., cholestasis) should be recorded on the Adverse Event eCRF.

If a clinically significant laboratory abnormality is not a sign of a disease or syndrome, the abnormality itself should be recorded on the Adverse Event eCRF, along with a descriptor indicating whether the test result is above or below the normal range (e.g., "elevated potassium," as opposed to "abnormal potassium"). If the laboratory abnormality can be characterized by a precise clinical term per standard definitions, the clinical term should be recorded as the adverse event. For example, an elevated serum potassium level of 7.0 mEq/L should be recorded as "hyperkalemia."

Observations of the same clinically significant laboratory abnormality from visit to visit should only be recorded once on the Adverse Event eCRF (see Section [5.3.5.3](#) for details on recording persistent adverse events).

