6.5 SAFETY ANALYSES

The safety analysis population will consist of all randomized patients who received at least one dose of study drug, with patients grouped according to treatment received.

Safety will be assessed through summaries of exposure to study treatment, adverse events, changes in laboratory test results, and changes in vital signs and ECGs. All verbatim adverse event terms will be mapped to Medical Dictionary for Regulatory Activities thesaurus terms, and adverse event severity will be graded according to DAIDS toxicity grading scale (see Section 5.3.3 and [Appendix 10](#)). All adverse events, serious adverse events, adverse events leading to death, adverse events of special interest, and adverse events leading to study treatment discontinuation that occur on or after the first dose of study treatment (i.e., treatment-emergent adverse events) will be summarized by mapped term, appropriate thesaurus level, and severity grade. Relevant laboratory, vital sign (pulse rate, respiratory rate, BP, pulse oximetry, and temperature), and ECG data will be displayed by time, with grades identified where appropriate.

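### In this crossover, a non-serious adverse event that bridges the washout and worsens in Period 2 may have its worst grade counted under the wrong treatment, because no date of worsening and no attribution rule are specified

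*Combined protocol and SAP*

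**What the plan says.** **Recording.** Section 5.3.5.3 says of an event that continues without resolution: "Such events should only be recorded once on the Adverse Event eCRF". Its starting grade is kept: "The initial severity (intensity or grade) of the event will be recorded at the time the event is first reported". The worst grade is kept as well: "If a persistent adverse event becomes more severe, the most extreme severity should also be recorded on the Adverse Event eCRF". If the event turns serious, the site updates the record, "providing the date that the event became serious". No date is requested for a grade increase that does not make the event serious. An event that resolves and returns is treated differently: "Each recurrence of an adverse event should be recorded as a separate event on the Adverse Event eCRF". Section 5.3.5.4 applies the once-only rule to laboratory events ("Observations of the same clinically significant laboratory abnormality from visit to visit should only be recorded once on the Adverse Event eCRF"), Section 5.3.5.5 does the same for vital signs, and both refer back to Section 5.3.5.3.

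**Analysis.** Section 6.5 groups patients by treatment received. It takes events "that occur on or after the first dose of study treatment (i.e., treatment-emergent adverse events) will be summarized by mapped term", thesaurus level and severity grade. Laboratory, vital-sign and ECG data are displayed by time. Section 6.4 groups patients by the treatment of a given period, but that text concerns efficacy.

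**Endpoint.** The first safety endpoint in Table 1 (Section 2) is "Incidence and severity of adverse events, with severity determined according to the DAIDS toxicity grading scale".

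**The concern.** The recording rule suits a parallel-group trial, where a patient has one treatment and the worst grade can only belong to it. Here every completer receives both treatments, and under Section 5.3.1 adverse event reporting runs without a break from first dose to 28 days after the last. For an event that crosses from one period to the other, treatment received does not by itself say which treatment should carry the worst grade.

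Section 5.2.1 counts a worsening in the severity of a known condition as an adverse event, yet Section 5.3.5.3 opens no new record for it. The rule for preexisting conditions (Section 5.3.5.8) does not help, because it covers only conditions present at screening.

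At stake is the severity comparison in the drug's first use in patients. If GDC-6599 aggravates ongoing symptoms, attribution by onset date would move those worse grades to placebo in the placebo-first sequence. A date that was not collected may be hard to recover afterwards, so this cannot be left to the programming stage.

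**Working it through.** The plan gives no figure on this point to reproduce. The check applies the two sections to example records, then shows how any effect would scale.

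**Timing.** Section 4.3.2 puts Visit 4 at Day 14 and Visit 5 at Day 30. The dosing gap is 30 − 14 = 16 days. Table 4 (Section 5.1.3.2) equates 5 half-lives with about 4 days, so one half-life is 4/5 = 0.8 day. The gap is 16/0.8 = 20 half-lives, and the fraction of drug left is 2^−20, about 1 in a million. A worsening after Day 30 therefore occurs under the Period 2 treatment.

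**Example records.**
- Placebo first; Grade 1 symptom from Day 10, unresolved; Grade 2 on Day 33 on GDC-6599; not serious. The record holds the onset, Grade 1 and Grade 2, with no date for Grade 2. If the worst grade follows the onset date, placebo carries Grade 2 and GDC-6599 carries nothing. If it follows the period of worsening, placebo carries Grade 1 and GDC-6599 Grade 2. Section 6.5 does not choose, and the required data cannot support the second option.
- GDC-6599 first, same course: the mirror image.
- Resolves in washout, returns in Period 2: two records, correctly placed.
- Becomes serious in Period 2: dated.
- Reaches Grade 3 and is judged clinically significant: an adverse event of special interest (Section 5.2.3), reported within 24 hours of the investigator learning of it (Section 5.4). With a 16-day gap, the report usually identifies the period.

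The unplaced remainder is mainly Grade 1-to-2 worsening and Grade 3 or higher worsening not judged clinically significant.

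**How often (assumed; no rate is in the documents).** Let w be the share of patients with an event that bridges the washout and worsens. The expected number is n × w, and the chance of at least one is 1 − (1 − w)^n.

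| w | n = 80: expected, chance of at least one | n = 40 (one sequence): expected, chance of at least one |
|---|---|---|
| 1% | 0.8, 55% | 0.4, 33% |
| 2.5% | 2, 87% | 1, 64% |
| 5% | 4, 98% | 2, 87% |
| 10% | 8, about 100% | 4, 98% |

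**Effect on the comparison if worst grades followed onset date (assumed).** Take 80 patients, 40 per sequence, and new-onset Grade 3 or higher events in 6% of GDC-6599 periods and 3% of placebo periods. Let b be the share with an event ongoing at the first Period 2 dose, and d and p the chances that it then escalates to Grade 3 or higher on drug and on placebo.
- By period of worsening: drug 80 × 0.06 + 40bd; placebo 80 × 0.03 + 40bp.
- By onset: the terms 40bd and 40bp change places.
- The drug excess therefore falls by 2 × 40b(d − p) = 80b(d − p).

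| b | d = 30%, p = 10%: excess by period, by onset | d = 6%, p = 3%: excess by period, by onset | d = p |
|---|---|---|---|
| 0 | 2.4, 2.4 | 2.4, 2.4 | 2.4, 2.4 |
| 5% | 2.8, 2.0 | 2.46, 2.34 | 2.4, 2.4 |
| 10% | 3.2, 1.6 | 2.52, 2.28 | 2.4, 2.4 |
| 20% | 4.0, 0.8 | 2.64, 2.16 | 2.4, 2.4 |

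At b = 10% the loss is half under the first pair of escalation rates and about 10% (0.24/2.52) under the second. The result depends on d − p, for which the documents give no value. The table also ignores the dated reports for clinically significant Grade 3 or higher events, so it overstates the exposure at that level.

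**The case against.** A reader might infer that the plan charges the worst grade to the treatment at onset, so that severe drug events are booked to placebo. No section states that rule. Section 6.5 is silent on events spanning periods, and the initial grade and the date of seriousness are both kept.

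A reader might also infer that the excess of severe events on drug would be halved. That needs an escalation rate of 30% on drug against 10% on placebo, which nothing in the documents supports. It also counts events that usually have a dated report. Further, Section 4.6.1 stops treatment for clinically significant Grade 3 or higher events judged related, Section 6.5 summarises discontinuations separately, and Section 7.1 keeps eCRF corrections in an audit trail. The unblinded Internal Monitoring Committee reviews cumulative events (Section 3.1.2), so detection does not rest on the final tables alone.

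The affected set is narrow, the analyses are not formal tests, and the eCRF completion manual mentioned in Section 7.2 is not among the documents, so a field for the date of a grade change cannot be excluded.

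Most of this stands and limits the point. It does not remove it: special-interest events go onto the same adverse event form (Section 5.4.2.2), no rule carries the report date into the summary, and lower-grade worsening has no comparable trail. Even with a date field, Section 6.5 would still need an attribution rule.

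**Conclusion.** The point holds as a gap in recording and attribution. From the data the protocol requires, a non-serious worsening in Period 2 of an event carried over from Period 1 cannot be reliably placed, so its worst grade may be counted under the wrong treatment. The documents do not show that it will be.

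The size is unknown and probably small. It depends on how many events stay unresolved across 16 days without dosing and on how far escalation differs between drug and placebo. With no bridging events nothing is misplaced. With equal escalation rates single events may be misplaced, but the expected drug-placebo difference does not change. The conclusion assumes that the eCRF asks for no more than Section 5.3.5.3 describes. The change is worth making because it is cheap and the missing dates may be hard to reconstruct.

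**What to change.** **Section 5.3.5.3:** for an event ongoing at the first Period 2 dose, require the date of any grade increase on or after that dose, with the grade before and after. Alternatively, open a new record with that date as onset, linked to the original. Sections 5.3.5.4 and 5.3.5.5 need no separate change, because they already refer to 5.3.5.3.

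**Section 6.5:** define treatment-emergent separately for each period and say to which period washout days belong. Count each event under a period's treatment at the worst grade reached in that period. Count an event carried into Period 2 for the Period 2 treatment only if its grade exceeds that at the first Period 2 dose.

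**Cost:** one recording instruction, a derivation rule in the safety programming, and a few extra date entries or linked records. No visits or patients are added. Linked records must not be counted as separate episodes.
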